3. INTERIM ANALYSIS AND DATA REVIEW COMMITTEE

3.1. Study Evaluation Team (SET)

A SET composed of study investigators and internal sponsor team members will convene (for all subjects in Part 1 and the first 2 subjects in each age group if not enrolled until Part 2) to evaluate the safety of ibrutinib in combination with CIT to determine if the dose is appropriate and when enrollment may start in the youngest age group. Safety review by the SET will include non-hematologic toxicities that required withholding study treatment for more than 10 days or cardiac rhythm abnormalities in those subjects receiving RVICI.

3.2. Data Monitoring Committee (DMC)

An independent DMC will be established to monitor data on an ongoing basis to ensure the continuing safety of the subjects enrolled in this study and review the interim analysis results. The DMC will consist of at least 1 medical expert in the relevant therapeutic area and at least 1 statistician. The DMC responsibilities, authorities, and procedures will be documented in its charter.

The committee will meet periodically to review interim data. After the review, the DMC will make recommendations regarding the continuation of the study. The details will be provided in a separate DMC charter. At the interim analysis, the DMC may recommend stopping the study for either futility or efficacy, if the pre-specified stopping boundary is crossed.

3.3. Interim Analysis

During Part 2, an external DMC will be used for the review of safety and will conduct an interim analysis. The pre-planned interim analysis will be conducted when approximately 30 EFS events are reached. An external DMC will determine the appropriateness for early stopping using the nonbinding stopping rules (Table 2) as well as other efficacy and safety endpoints. The 1-sided p-value required for early stopping for futility is ≥ 0.367 and efficacy is ≤ 0.006 if there are 30 EFS events at the interim analysis. This design employs the sequential testing approach as described by O'Brien and Fleming (1979)¹ to preserve the Type-I error rate.

Table 2: Stopping Boundaries (N=72 subjects, 2 Analyses)

Analysis Number	EFS events	Approximate Time	Number of Subjects	Cumulative Error		Stopping Boundary			
						p-value (1-sided)		Observed Hazard Ratio	
				Efficacy	Futility	Efficacy	Futility	Efficacy	Futility
Interim	30 (50%)	32 months	46	0.006	0.07	≤ 0.006	≥ 0.367	<0.378	≥ 0.878
Final	60 (100%)	50 months	72	0.050	0.2	≤ 0.048	-----	<0.632	-----

EFS=event-free survival.

4. SUBJECT INFORMATION

All statistical analyses will be performed using statistical analysis system (SAS[®]). Analyses of disposition, demographic, baseline disease characteristics, and prior and concomitant therapy will be conducted on the ITT population. Analyses of treatment compliance and extent of exposure will be conducted on the safety population. No statistical testing is planned.

Unless otherwise specified, all continuous endpoints will be summarized using descriptive statistics, which will include the number of subjects with a valid measurement (n), mean, standard deviation (SD), median, minimum, and maximum. All categorical endpoints will be summarized using frequencies and percentages. Percentages will be calculated by dividing the number of subjects with the characteristic of interest by the number of subjects in the analysis population.

4.1. Demographics and Baseline Characteristics

Subject demographics and baseline disease characteristics will be summarized using descriptive statistics.

- Demographics and baseline characteristics: age, sex, race, ethnicity, geographic region, height (cm), weight (kg), systolic blood pressure/diastolic pressure (SBP/DBP (mmHg), body surface area (m^2))

- Baseline disease characteristics: time from initial diagnosis to randomization; time from progression/relapse since last line of treatment to randomization; diagnosis (relapsed/refractory BL, Burkitt-like lymphoma, B-AL, diffuse large B-cell lymphoma (DLBCL), DLBCL not otherwise specified, or other pediatric mature B-cell NHL.); Lansky-Karnofsky performance status; cytopenia; Phosphor-BTK, as well as SYK, STAT3, caspase-3, BCL-xL, and cIAP1 expression; B-cell receptor (BCR)/CD79B, CARD11, and MYD mutations; c-MYC; immunoglobulin; T-cell receptor gene rearrangements; and drug acceptability and palatability assessment (Visual analog scale)
- Hematology: hemoglobin, platelet count, white blood cell count, absolute neutrophil count, absolute lymphocyte count
- Chemistry: sodium, potassium, blood urea nitrogen, creatinine, aspartate aminotransferase, albumin, alkaline phosphatase, total bilirubin, lactic acid dehydrogenase, uric acid, alanine aminotransferase

4.2. Subject Disposition

Disposition information will be summarized for the ITT population and safety population. Subject enrollment will be summarized by region, country, and investigator. The number of subjects undergoing, discontinuing, and completing the study treatment as well as their reasons for treatment discontinuation will be summarized.

Descriptive statistics will be provided for time on study. Time on study is defined the same way as OS with reversed censoring, ie, subjects who died will be censored. Based on this definition, time on study is the same as length of follow up. The Kaplan-Meier method will be used to estimate the median time on study.

4.3. Exposure Related Definitions

Treatment duration is the interval between date of first dose and end-of-treatment date. If date of end of treatment is not available, use last available treatment date.

Number of treatment cycles = the last cycle number - the first cycle number + 1.

The individual anticancer drugs that make up study treatment should be summarized separately. For the treatment phase, dosing information includes total dose received (the sum of actual dose administered), average dose level per administration (the ratio of total dose and treatment duration in cycles), and relative dose intensity:

$$\frac{\text{Sum of actual dose administered}}{\text{planned total cumulative dose for the regimen}}$$

Use the highest level of dose reduction to summarize categories - 'One dose reduction' and 'Two dose reductions'.

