Subjects in Part 1 will receive ibrutinib in combination with background CIT (investigator choice of RICE or RVICI) for 3 treatment cycles. Subjects in Part 2 will be randomized in a 2:1 ratio to receive either ibrutinib in combination with CIT (RICE or RVICI) or CIT alone, for 3 treatment cycles. The RICE regimen is comprised of cumulative doses as follows: rituximab 750 mg/m², ifosfamide 9 g/m², carboplatin 635 mg/m², etoposide 300 mg/m², and dexamethasone 100 mg/m². The RVICI regimen is comprised of cumulative doses as follows: rituximab 750 mg/m², vincristine 1.6 mg/m², idarubicin 20 mg/m², carboplatin 800 mg/m², ifosfamide 10 g/m², and dexamethasone 100 mg/m² (all doses represented as total administered in 1 cycle). For both regimens, triple intrathecal therapy consisting of methotrexate, corticosteroid, and cytarabine will be administered for central nervous system prophylaxis in age-appropriate dosing. Subjects with central nervous system disease will receive additional doses of triple intrathecal therapy. Cycles will be 28 days long, but may be shortened to 21 days. Study treatment will continue for 3 cycles, unless the subject experiences unacceptable toxicity or disease progression. Upon completion of 3 cycles of combination therapy, subjects randomized to ibrutinib having a response of PR or better will continue on ibrutinib monotherapy at the same daily dose for three 28-day cycles or until disease progression or unacceptable toxicity, or up until initiating subsequent antilymphoma therapy or a conditioning regimen for stem cell transplantation, whichever comes first.

Subjects who discontinue any component of CIT without disease progression will continue ibrutinib and remaining CIT components until 3 cycles are completed. If ibrutinib is discontinued for any reason, any remaining study treatment (RICE/RVICI) may continue. Ibrutinib should be temporarily stopped for any unmanageable, potentially study drug-related toxicity that is Grade ≥ 3 in severity until recovery to Grade ≤ 1 or baseline.

EFFICACY EVALUATIONS/ENDPOINTS

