The Treatment Phase will extend from enrollment (in Part 1) or randomization (in Part 2) until 1 of the following: 1) completion of 3 cycles of therapy, 2) transplantation, if clinically indicated, or 3) PD, whichever comes first. Cycles will be 28 days long; however, if count recovery occurs quickly and the investigator deems a subject ready to proceed with the next cycle of therapy, cycles can be shortened to as few as 21 days. As long as there is no disease progression after Cycle 1 or 2, a second and third cycle of therapy will be given, respectively. All subjects will receive background therapy with RICE or RVICI during the Treatment Phase.

The investigator will evaluate sites of disease by radiological imaging, physical examination, or other procedures as necessary, including but not limited to review of hematology, clinical chemistry, and lumbar puncture results. Assessment of tumor response and progression will be according to the International Pediatric NHL Response Criteria. The primary efficacy analysis of EFS will be based on assessment by an Independent Review Committee (IRC). At each site visit, subjects will undergo safety evaluations. Safety evaluations will include adverse event monitoring, physical examinations, concomitant medication usage, and clinical laboratory parameters. Population pharmacokinetics will be performed during Part 1 using a sparse sampling approach. Additional sparse pharmacokinetic samples will be collected during Part 2 to expand the pediatric pharmacokinetic dataset. Blood samples will be obtained for pharmacodynamic assessments (BTK occupancy) and for protein binding (Part 1 only).

[figure not shown]
Subjects will begin the Posttreatment Phase after completion of combination therapy. During the Posttreatment Phase, subjects on ibrutinib having a response of PR or better and have completed 3 cycles of combination treatment will continue on ibrutinib monotherapy at the same daily dose for three 28-day cycles, or until disease progression or unacceptable toxicity, or up until initiating subsequent antilymphoma therapy or a conditioning regimen for stem cell transplantation, whichever comes first. Follow-up visits to assess disease progression will be required if study treatment is discontinued prior to PD (including subjects who go on to transplant) and will be completed as per [Table 3](#) and [Table 4](#) until PD, the clinical cutoff for the

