4.4. Extent of Exposure

Descriptive statistics (n, mean, standard deviation, median, and range) will be provided for total number of cycles, treatment duration, and dosing information for all study medications (ibrutinib, rituximab, ifosfamide, carboplatin, etoposide, vincristine, idarubicin, and dexamethasone).

The number and percentage of subjects with dose reduction and dose interruption will be summarized. In addition, subjects with dose modifications and reasons for dose modifications will be summarized.

Details of exposure related definition is specified in Section [4.3](#).

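### SAP 4.3 labels dose per cycle as dose per administration, and its relative dose intensity has no time term, so delays cannot change it

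*SAP*

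**What the plan says.** SAP 4.3 gives three dosing summaries for the Treatment Phase, each calculated separately for each drug.

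- **Total dose:** the "sum of actual dose administered".
- **Average dose:** "average dose level per administration (the ratio of total dose and treatment duration in cycles").
- **Relative dose intensity (RDI):** that same total divided by the "planned total cumulative dose for the regimen".

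The section also defines the two quantities that could carry time: "Treatment duration is the interval between date of first dose and end-of-treatment date", and "Number of treatment cycles = the last cycle number - the first cycle number + 1". The RDI ratio uses neither.

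SAP 4.4 refers back to 4.3 and calls for "dosing information for all study medications (ibrutinib, rituximab, ifosfamide, carboplatin, etoposide, vincristine, idarubicin, and dexamethasone"). Neither document gives another definition of the average dose or of RDI.

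The protocol does not fix the calendar at three 28-day cycles. Section 3.1 says "cycles can be shortened to as few as 21 days" if counts recover quickly. Section 6.2.1 lets the start of a new cycle be postponed week by week for toxicity, with ibrutinib continuing meanwhile.

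**The concern.** The unit of the average-dose formula does not match its name. Dividing a total dose by a number of cycles gives dose per cycle. Most drugs here are given several times per cycle and the number differs by drug, so a reader of the exposure table cannot undo the error with one correction.

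The RDI formula measures how much was given, not how fast. This is an add-on trial with the same backbone options in both arms, so one natural question is whether adding ibrutinib slowed delivery of that backbone. The summary named for intensity gives the same answer whether the cycles ran on time or late. For ibrutinib, which is taken daily, the ratio moves with cycle length even when every daily dose is taken, and the SAP does not say how many days count as planned.

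**Working it through.** **1. Per-cycle totals.** Inputs are the single or daily doses and dosing days in Protocol Tables 5 and 6. Formula: dose × dosing days per cycle. For RICE this gives rituximab 375 × 2 = 750, ifosfamide 3 g × 3 = 9 g, carboplatin 635 × 1 = 635, etoposide 100 × 3 = 300 and dexamethasone 20 × 5 = 100. These reproduce the Protocol Synopsis totals: "rituximab 750 mg/m², ifosfamide 9 g/m², carboplatin 635 mg/m², etoposide 300 mg/m², and dexamethasone 100 mg/m²". The RVICI totals also reproduce: rituximab 750, vincristine 0.4 × 4 = 1.6, idarubicin 10 × 2 = 20, carboplatin 200 × 4 = 800, ifosfamide 2 g × 5 = 10 g, dexamethasone 100.

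**2. Average dose, full dosing for 3 cycles.** SAP value = total ÷ 3 cycles. Per-administration value = total ÷ number of administrations. All values are per m².

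| Drug | SAP value | Per administration | Ratio |
|---|---|---|---|
| Rituximab | 750 mg | 375 mg | 2 |
| Idarubicin (RVICI) | 20 mg | 10 mg | 2 |
| Etoposide (RICE) | 300 mg | 100 mg | 3 |
| Ifosfamide (RICE) | 9 g | 3 g | 3 |
| Ifosfamide (RVICI), by dosing day | 10 g | 2 g | 5 |
| Dexamethasone, by day | 100 mg | 20 mg | 5 (15 by divided dose) |
| Vincristine (RVICI), by dosing day | 1.6 mg | 0.4 mg | 4 |
| Carboplatin (RVICI), by dosing day | 800 mg | 200 mg | 4 |
| Carboplatin (RICE) | 635 mg | 635 mg | 1 |
| Ibrutinib, 28-day cycles | 329 × 84 ÷ 3 = 9,212 mg | 329 mg | 28 |
| Ibrutinib, 21-day cycles | 329 × 63 ÷ 3 = 6,909 mg | 329 mg | 21 |

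If a 4-day continuous infusion counts as one administration, the ratio for RVICI vincristine and carboplatin is 1.

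**3. RDI for CIT at full dose.** SAP ratio = actual total ÷ planned total = 1.00 whatever the timing. Time-based RDI = (actual dose ÷ actual time) ÷ (planned dose ÷ planned time). At full dose this reduces to planned time ÷ actual time, with planned time 3 × 28 = 84 days.

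| Scenario | Actual days | SAP ratio | Time-based |
|---|---|---|---|
| On schedule | 84 | 1.00 | 1.00 |
| Cycles 2 and 3 each 1 week late | 98 | 1.00 | 84/98 = 0.86 |
| Cycles 2 and 3 each 2 weeks late | 112 | 1.00 | 84/112 = 0.75 |
| Three 21-day cycles | 63 | 1.00 | 84/63 = 1.33 |

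**4. RDI for ibrutinib at the full daily dose throughout.** Assumption: the planned total is fixed at 84 daily doses. Three 21-day cycles give 63/84 = 0.75. Ibrutinib continued through two 2-week CIT delays gives 112/84 = 1.33. Dose per day is 100% of plan in both. If the planned days instead follow the subject's own 21-day cycles, the first ratio is 63/63 = 1.00.

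**5. Early stopping.** One full cycle given on time, then stop: the cumulative ratio is 1/3 = 0.33 if three cycles are the planned total, while time-based RDI over those 28 days is 1.00.

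**The case against.** The strongest reply is that the RDI ratio is a sound measure under the wrong name. It is a valid percent of planned cumulative dose and equals the time-based form when all three cycles run on the 28-day schedule. It also shows early stopping, which the time-based form can hide (step 5). It drops when a drug is left out: under Protocol 6.2.1, a drug whose toxicity persists after a 2-week delay stays stopped while the cycle restarts with the others. All of this stands, and it is a reason to keep the ratio.

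A reader might infer more than the documents support in four ways.

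- **That delays are invisible and backbone delivery cannot be assessed.** SAP 4.4 also summarises treatment duration, number of cycles, interruptions, and modifications with reasons. Duration read beside cycle count signals delay.
- **That 2-week delays mean a true intensity of 28/42 = 0.67.** That needs all three cycles to last 42 days. With three cycles, only the starts of Cycles 2 and 3 can be delayed, which gives 0.75.
- **That 21-day cycles make every drug look 75% dosed.** This can arise only for ibrutinib, and only with an 84-day denominator that the SAP does not state. Full-dose CIT scores 1.00.
- **That every per-administration value is wrong.** RICE carboplatin is right, and the 4-day RVICI infusions are right if each counts as one administration.

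**Conclusion.** The point holds for both definitions, with limited reach. The average-dose formula gives dose per cycle and overstates dose per administration from 2-fold (rituximab, idarubicin) to 28-fold (ibrutinib in 28-day cycles), apart from the exceptions named above. This rests only on the protocol's dosing tables and on reading duration in cycles as the number of cycles.

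The RDI formula cannot register a delay: 1.00 against 0.75 for full-dose CIT with two 2-week delays. The ibrutinib figures of 0.75 and 1.33 depend on the assumed 84-day denominator. That the SAP leaves this open is itself a gap.

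Only descriptive exposure tables are affected. The EFS analysis, alpha, power and stopping boundaries are untouched. This is a minor but clear correction.

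**What to change.** Four changes to SAP 4.3:

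1. Divide total dose by the number of administrations, stating how continuous infusions and divided doses are counted; or keep the formula and relabel it average dose per cycle.
2. Relabel the current ratio percent of planned cumulative dose and keep it. State whether the planned total covers three cycles or only the cycles started.
3. Add a time-based RDI: (actual dose ÷ actual time) ÷ (planned dose ÷ planned time), with planned dose and planned time on the same basis. Mixing them creates a new error. For ibrutinib in three 21-day cycles, a 63-day planned dose over a 12-week planned time gives (63/9) ÷ (63/12) = 1.33 for a subject dosed exactly as intended.
4. For ibrutinib, compare the actual dose with the planned daily dose times the days in the subject's actual per-protocol cycles.

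The cost is SAP wording and table programming. Protocol Section 6 already requires all dosing to be recorded in the CRF, and Section 7.2 requires each CIT administration to be recorded, so no new data are needed. No dose, schedule or treatment rule changes.

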4.4. Extent of Exposure

Descriptive statistics (n, mean, standard deviation, median, and range) will be provided for total number of cycles, treatment duration, and dosing information for all study medications (ibrutinib, rituximab, ifosfamide, carboplatin, etoposide, vincristine, idarubicin, and dexamethasone).

The number and percentage of subjects with dose reduction and dose interruption will be summarized. In addition, subjects with dose modifications and reasons for dose modifications will be summarized.

Details of exposure related definition is specified in Section [4.3](#).

4.5. Protocol Deviations

Subjects with eligibility and major protocol deviations will be listed by treatment group.

Protocol deviations will be based on clinical review, but not limited to, the following aspects: (1) eligibility criteria, (2) patient safety, (3) efficacy assessment deviation, and (4) treatment compliance. Protocol deviations will be closely monitored during the execution of the study and the final set of protocol deviation criteria will be finalized before database lock.

4.6. Prior and Concomitant Medications

For summarization purposes, medications will be coded to a generic term based on the World Health Organization (WHO) dictionary. Medications administered prior to the first dose of study medication will be considered prior medications. Concomitant therapies include those taken on or after first dose date through the date of last dose of study drug. Using this definition, a medication can be classified as both prior and concomitant.

Incidence of prior and concomitant medications will be summarized by Anatomical Therapeutic Chemical (ATC) class and drug generic term. Prior anticancer therapy will be summarized by type (eg, radiotherapy, surgery, chemotherapy). Best response to last line of prior therapy will also be summarized.

The following concomitant medications of special interest will also be summarized:

- Anti-coagulation and anti-platelets.
- CYP3A inhibitors/inducers
- Growth factors/ cytokines by background therapy
- Transfusions

5. EFFICACY

Analysis of efficacy endpoints will be conducted on the ITT population. [Table 3](#) summarizes the efficacy endpoints and analysis methods to be performed.

Table 3: Summary of Efficacy Analyses to be Performed

Endpoint	Analysis	Analysis Method	Population
Primary			
Event-free Survival (EFS) as assessed by IRC	Primary	Non-stratified log-rank test, non-stratified Cox regression model, all PD and death considered as events regardless of subsequent antilymphoma therapy or a conditioning regimen for stem cell transplantation. EFS is defined as the time interval from randomization to death, disease progression, or lack of CR or PR after 3 cycles of treatment.	ITT
	Sensitivity	
 1) Alternative censoring rule 1: subjects who received subsequent antilymphoma therapy or a conditioning regimen for cell transplantation are considered to have had an EFS event at the initiation of subsequent therapy 2) Alternative censoring rule 2: subjects who received subsequent antilymphoma therapy or a conditioning regimen for cell transplantation are censored at the last disease assessment showing no evidence of PD before the use of subsequent therapy 3) Alternative censoring rule 3: subjects will be censored at the last disease assessment if they progress, die or have not responded after missing ≥ 2 planned disease assessment visits. 4) Investigator assessed EFS by non-stratified log-rank test and non-stratified Cox regression model; concordance rate between the IRC-determined EFS and investigator-determined EFS 	ITT
	Subgroup	Non-stratified Cox regression model within each subgroup	ITT
Secondary			
Long-term survival (EFS) at 2 and 3 years		IRC assessed chi-square test for 2 and 3 year EFS rate.	ITT
Overall Survival	Primary	Non-stratified log-rank test, non-stratified Cox regression model, as the time interval from enrollment (Part 1) or randomization (Part 2) to all deaths considered as events regardless of subsequent antilymphoma therapy or a conditioning regimen for stem cell transplantation.	ITT
	Sensitivity	Censored at subsequent antilymphoma therapy or a conditioning regimen for stem cell transplantation.	
Overall Response in Part 1	Subgroup	Non-stratified Cox regression model within each subgroup Listing of IRC and investigator assessments for those subjects who respond.	ITT Enrolled subjects
Overall Response Rate in Part 2	Primary	IRC assessed ORR chi-square test, Logistic regression model	ITT subjects with measurable disease at baseline
	Sensitivity	Investigator assessed ORR chi-square test, Logistic regression model	
	Subgroup	Logistic regression model	
Tumor Volume Reduction Rate		Analysis of variance (t-test) for percent decrease in the sum of the products of the lesion diameters at Day 14	ITT subjects with measurable disease at baseline
Time to Response		Non-stratified log-rank test, as the time interval from randomization to response for those subjects who respond as	ITT subjects who responded

Table 3: Summary of Efficacy Analyses to be Performed

Endpoint	Analysis	Analysis Method	Population
		assessed by IRC.	
Duration of Response		Non-stratified log-rank test, as the time interval from date of initial documentation of a response to the date of first documented evidence of progressive disease (PD) or death as assessed by IRC.	ITT subjects who responded
Rate of Subjects Who Proceed to Stem Cell Transplantation		Chi-square test for percent of subjects who proceed to stem cell transportation, Logistic regression model.	ITT
Other			
Subsequent Therapy		Descriptive summary Non-stratified log-rank test for the effect of subsequent antilymphoma therapy or a conditioning regimen for stem cell transplantation on overall survival, will be performed, as appropriate.	ITT subjects
Risk factors		Non-stratified Cox proportional hazards model using covariates to analyze the effect on EFS and survival will be performed, as appropriate.	ITT

